Implementation of an ERAS program in patients undergoing thoracic surgery at a third-level university hospital. An ambispective cohort study.

(Short title: ERAS implementation in thoracic surgery)

31/12/2019

NCT ID not yet assigned

METHODS

Study design and participants

This study analyzes the implementation of an ERAS program in a thoracic service of a third level hospital (*Hospital Fundación Jiménez Díaz, Madrid, Spain*). To this end, we designed an ambispective cohort study, with a prospective arm of patients undergoing thoracic surgery within an ERAS program versus a retrospective arm of patients before the implementation of the protocol. Our centre's ethics committee approved our study before the start of patient recruitment, January 2018 Ref: EO071-18_FJD. This study followed the Strengthening the Reporting of Observational Studies in Epidemiology ([STROBE](#)) reporting guideline for cohort studies¹³.

After informed consent, we included patients consecutively since the implementation, except those who refused the inclusion in the study or were under 18 years old. We also asked for informed consent from the patients who were part of the retrospective cohort. For the calculation of the required sample size, we assumed that the ERAS program would result in a 25% reduction in the absolute risk of suffering a surgical complication. Since the surgical complication rate for our patients in 2016 was 40%, a type-I error of 5% and a power of 80% would require 47 patients per arm.

Procedures

We recruited 50 patients throughout 2018 and 2019 and compared them with data from the last 50 patients in 2016, the year in which we knew the surgical complication rate. We followed up each patient for 30 days after surgery through hospital and primary care medical records. Demographic and comorbidity data were collected from all patients, from which we calculated Charlson's comorbidity index¹⁴ for all patients.

We designed our centre's ERAS program through different measures during the preoperative, intraoperative and postoperative period. During the preoperative period, the patients and their families received comprehensive multidisciplinary information about the protocol, as well as their daily goals and expected discharge date. Also, a team

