specialized in therapy against lung diseases taught patients pulmonary expansion exercises to be carried out until surgery was performed. Smoking cessation and nutritional screening of the patient were also part of this stage.

The patients underwent video-assisted thoracoscopic surgery (VATS), whenever possible, leaving a chest tube at the end of the surgery. All subjects received antibiotic and antithrombotic prophylaxis. Intraoperative management of patients was performed under general anaesthesia combined with regional techniques for pain control, avoiding the use of benzodiazepines and opioids. Those patients in whom thoracic epidural catheter was implemented during surgery continued its use through a patient-controlled analgesia system. Besides, a hot air system warmed the patients during surgery to maintain normothermia. Extubation was performed as soon as possible after the end of the surgery, and we encouraged early removal of the urinary catheter.

From the time of extubation, the patients began oral tolerance and respiratory physiotherapy exercises. Also, the patients were allowed to walk around early. The patients were discharged when they were free of complications, without severe pain, urinary catheter or chest tube.

Outcomes

The primary outcome was the number of patients with 30-day surgical complications. We defined air leakage, bleeding, infection, and reintervention as surgical complications. Secondary outcome included ERAS adherence, no-surgical complications, mortality, readmission, reintervention rates, pain (defined as any level of pain that prevents early ambulation) and hospital lenght of stay. To evaluate ERAS adherence, we defined seven items: VATS approach, regional analgesia, oral tolerance within 6 hours, urinary catheter removal within 24 hours, ambulation within 24 hours, respiratory physiotherapy within 24 hours and chest tube removal within 48 hours.

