## Statistical analysis

We analyzed outcomes depending on whether the patient belonged to the ERAS program or the retrospective standard cohort. The discrete and continuous variables were described as number and percentage and median (interquartile range [IQR]) and their differences analyzed using the Pearson test or the Wilcoxon rank-sum tests. Subsequently, according to the adherence rate to ERAS items (regardless of whether the patients belonged to the ERAS or the retrospective standard cohort), We performed a multivariate logistic analysis to study the association of complication rates, readmission or pain with ERAS adherence, clinical and demographic data, presenting the results in forest plots as odds ratio with 95% confidence interval. Similarly, we used Cox regression for multivariate analysis of length of stay, presenting the results in forest plot as hazard ratio with 95% confidence interval. To avoid errors by multiple comparisons, we calculated the respective q-value for each p-value to maintain a false discovery rate below 5%. We considered comparisons in which p-value and q-value were below .05 as being statistically significant.

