## RESULTS

No patient declined inclusion in the study. The demographic characteristics and comorbidities of the patients are shown in Table 1. The two cohorts were not totally homogeneous, with a higher number of patients with hypertension in the standard cohort [26 (52%) vs ERAS 15 (30%),  $p = 0.03$ ] and chronic obstructive pulmonary disease [12 (24%) vs ERAS 4 (8%),  $p = 0.02$ ]. Although the number of patients with ASA class  $> 2$  was higher in the standard group [26 (52%) vs ERAS 15 (30%)], we found no difference between the cohorts in Charlson's comorbidity index. We included these three items, along with age and sex in the subsequent multivariate analyses.

Data on ERAS adherence and compliance for each of the protocol items are shown in Table 2. Adherence to the ERAS protocol was significantly higher in the prospective than in the retrospective cohort [Median: Standard 0.29 (0.14-0.43) vs ERAS 0.71 (0.57-0.82),  $p < 0.001$ ]. The VATS approach was greater in the ERAS group [29 (58%) vs Standard 11 (22%),  $p < 0.001$ ], and the number of patients who ambulated on the first postoperative day [40 (80%) vs Standard 0 (0%),  $p < 0.001$ ], but no difference was found in the use of regional analgesia. Also, the times to oral intake and removal of the urethral catheter were lower in the ERAS group [Median (h): Standard 24 (24-24) vs ERAS (6-7.5), and Standard 48 (24-48) vs ERAS 19 (6-24), respectively].

The primary and secondary results are shown in Table 3. We found no difference between the two groups in either surgical complications [Standard 18 (36%) vs 12 (24%),  $p = 0.19$ ], non-surgical complications [Standard 21 (42%) vs 12 (24%),  $p = 0.06$ ] or length of stay [Median (days): Standard 4 (3-6) vs 4 (3-5),  $p = 0.19$ ], and the ERAS group was significantly lower only in its readmission rate [Standard 15 (30%) vs 6 (12%),  $p = 0.03$ ]. No deaths were recorded in the ERAS group, compared to two deaths in the retrospective cohort.

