Multivariate analyses are shown in Figures 1, 2 and 3. ERAS adherence was the only factor associated with a reduction in surgical complications [OR (95%CI) = 0.02 (0.00, 0.59),  $p = 0.03$ , Figure 1A], and postoperative pain [OR (95%CI) = 0.01 (0.00, 0.28),  $p = 0.01$ , Figure 2B]. It was also associated with a lower readmission rate [OR (95%CI) = 0.01 (0.00, 0.24),  $p = 0.007$ , Figure 2A] and an increased likelihood of discharge from the hospital [HR (95%CI) = 18.5 (4.39, 78.4),  $p < 0.001$ , Figure 3]. The thoracic epidural analgesia was the only factor that showed an association with lower rates of non-surgical complications [OR (95%CI) = 0.09 (0.01, 0.49),  $p = 0.008$ , Figure 1B]. It was also associated with lower rates of postoperative pain [OR (95%CI) = 0.16 (0.03, 0.86),  $p = 0.03$ , Figure 2A] and increased probability of discharge from the hospital [HR (95%CI) = 3.14 (1.39, 7.07),  $p = 0.006$ , Figure 3]. The intercostal blockade also increased the latter likelihood [HR (95%CI) = 7.55 (2.94, 19.3),  $p < 0.001$ , Figure 3].

No significant  $p$ -value was rejected after the calculation of  $q$ -value within the multiple comparability study.

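### The 80% power is for one unadjusted 5% test, but the significance rule adds q<.05 with no family named; readmission and two p=0.03 model claims depend on that choice

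*SAP*

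**What the plan says.** The protocol (Study design and participants) assumes a fall in surgical complications from 40% by 25 points, and states that "a type-I error of 5% and a power of 80% would require 47 patients per arm". It mentions no allowance for multiplicity and does not state sidedness. Fifty patients per cohort were used.

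Under Outcomes, the primary is surgical complications within 30 days. "Secondary outcome included ERAS adherence, no-surgical complications, mortality, readmission, reintervention rates, pain" begins the secondary list, which ends with length of stay. That makes seven secondary outcomes and eight in all.

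The SAP (Statistical analysis) says "we calculated the respective q-value for each p-value to maintain a false discovery rate below 5" percent, and then: "We considered comparisons in which p-value and q-value were below .05 as being statistically significant". The q procedure is identified only by a citation. The family and its number of tests are not given, and the primary is not set apart.

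The SAP's RESULTS section reports that "the ERAS group was significantly lower only in its readmission rate" and, from the models, that "ERAS adherence was the only factor associated with a reduction in surgical complications" (p=0.03). Epidural analgesia with less pain is also reported at p=0.03. The section closes by saying that every significant p-value survived the q-value step "within the multiple comparability study". The text shows no q-value.

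**The concern.** The sample size and the significance rule describe different tests. Requiring q<.05 on top of p<.05 can only lower power or leave it unchanged, so a power figure for p<.05 alone does not carry over.

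The more practical issue is the undefined family. A q-value depends on which other p-values are ranked with it. The citation may supply a procedure, but it cannot say which of this study's tests were pooled. For p-values near .03, that choice decides the result. Readmission is the only clinical outcome reported as significantly different between cohorts. The adherence association is the only significant finding reported for surgical complications, the primary outcome. Both lie in that range.

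**Working it through.** **1. The plan's own figure.** Inputs from the protocol: 0.40 vs 0.15, 5%, 80%. The two-sided unpooled formula is n = (1.960 + 0.842)² × (0.40×0.60 + 0.15×0.85) / 0.25² = 46.15, so 47. This matches. A one-sided pooled formula with continuity correction also gives 47, so sidedness cannot be inferred from the figure. Exact power of the two-sided Pearson test is 0.793 at 47 per arm and 0.819 at 50.

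**2. Power for the primary with the q rule added.** Assumptions: BH, independent tests, 50 per arm, 40% vs 15% for the primary, and the eight named outcomes as the family. By simulation:

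| Other seven outcomes | Power for primary |
|---|---|
| all null | 0.555 |
| adherence certain, six null | 0.64 |
| about observed sizes | 0.69 |
| all at 40% vs 15% | 0.79 |
| no q rule (exact) | 0.82 |

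Observed sizes means adherence certain, 42 vs 24% (non-surgical complications), 30 vs 12% (readmission), 4 vs 0% (deaths), z=1.31 for length of stay, and pain and reintervention null. Other families or procedures give other values.

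**3. Readmission.** From 15/50 vs 6/50, Pearson p=0.0271. The BH q is the smallest value of m×p/rank at or beyond the test's own rank. Adherence is printed as p<0.001. Recomputed p-values are 0.0556 for non-surgical complications, 0.190 for surgical complications and 0.153 for mortality. Pain and reintervention are not printed; they are taken as p≥.05, because only readmission is reported as significant.

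- Seven secondary outcomes: 7×0.0271/2 = 0.095. If both unprinted p-values are as low as .05, non-surgical complications at rank 5 bring it to 7×0.0556/5 = 0.078.
- All eight outcomes: 8×0.0271/2 = 0.109, or 8×0.0556/5 = 0.089 on the same low assumption.
- The nine printed group comparisons (adding hypertension, COPD, VATS and ambulation, without mortality, pain and reintervention): p-values 0.0253, 0.0271 and 0.0291 take ranks 4 to 6, so q = 9×0.0291/6 = 0.044. With COPD at its printed 0.02 instead of the recomputed 0.0291, q = 9×0.0271/6 = 0.041.
- All 17 printed p-values (these nine plus eight model coefficients): 17×0.03/14 = 0.036.

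**4. The two p=0.03 model claims.** Eight coefficients have printed p-values: .03, .01, .007 and <.001 (adherence); .008, .03 and .006 (epidural); <.001 (intercostal). In a family of m coefficients that contains these eight, with all unprinted ones non-significant, both claims have q = m×0.03/8.

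- m=8: 0.030.
- m=40: 0.15. The 40 is an assumed count: eight terms (adherence, three baseline items, age, sex, epidural, intercostal) in five models. "We included these three items, along with age and sex in the subsequent multivariate analyses" supports five of those terms.
- Rounding: a printed .03 may be anything from .025 to .035. At .035, q is 0.048 for m=11 and 0.0525 for m=12. At .025, q is 0.047 for m=15 and reaches 0.05 at m=16.

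So these claims pass at about 11 coefficients or fewer and fail above about 15. Other groupings also disagree: adherence with surgical complications has q = 5×0.03/4 = 0.0375 across the five adherence coefficients, but 6×0.03/1 = 0.18 within a six-term model whose other terms are clearly null.

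**The case against.** The strongest reply is that the primary failed at p=0.19, before any q-value mattered. That stands. A reader might infer that the null primary is a product of a weakened test. The documents do not support this: the step it failed has about 82% power at 50 per arm under the design assumptions.

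A second reply is that the power figures rest on assumed families. That also stands. The all-null case treats adherence, which the programme is meant to change, as null. A family of 20 with only the primary non-null would give 42%. The figures show that the stated 80% does not belong to the combined rule; they do not bracket the true power.

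Third, a q procedure that estimates the share of true nulls can give smaller values than BH. It can, but with seven or eight tests the estimate turns on two unprinted p-values. Using the share of p>.5, readmission has q=0.054 if both exceed .5 and 0.027 or less otherwise. That is a reason to name the procedure.

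Fourth, the RESULTS section says nothing was lost, and families made only of printed p-values agree. A reader might infer from the failing families that the statement is false. That is not shown: q-values may stand in tables or figures that are not reproduced in the available text. Even so, printed q-values would not by themselves tell a reader which tests were pooled.

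**Conclusion.** The point holds as a mismatch between the sizing and the significance rule, together with an undefined family. The stated 80% applies to the unadjusted test only. Under BH over the eight named outcomes, power would be about 56% with the others null or 69% at about observed effects, against 82%; these are illustrations under independence and an assumed family.

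The conclusion on the primary does not change. The consequence is for the positive claims. Among the study's own secondary outcomes, readmission does not reach q<.05 under BH. In the BH families worked above, it does so only with baseline imbalances and adherence items in the ranking, and those tests carry no evidence about readmission. The two p=0.03 model claims depend on how many coefficients are counted, and because their p-values are rounded no exact cutoff can be given. Whether all significant results survived cannot be checked from the available text. This should be corrected, but it does not overturn the main result.

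**What to change.** - **Primary.** Test the between-cohort comparison once at two-sided 5%, outside the q-value procedure, and record that this was fixed after the data were seen. Alternatively, keep the rule and state that the 80% applies only to the unadjusted test.
- **Statistical analysis section.** Name the q procedure, including any null-proportion estimate, and the family actually used with its number of tests. Report the q-values.
- **Sensitivity analysis, disclosed as post hoc.** Give q for the secondary between-cohort outcomes without baseline tests and individual adherence items. Give q for the model coefficients as a separate family that counts all fitted terms.
- **Wording.** Describe a result as nominal if its q is not below .05.

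The cost is some SAP text and a short recalculation from existing p-values, with no new data. The downside is that readmission and the two p=0.03 model claims may become nominal.

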## RESULTS

No patient declined inclusion in the study. The demographic characteristics and comorbidities of the patients are shown in Table 1. The two cohorts were not totally homogeneous, with a higher number of patients with hypertension in the standard cohort [26 (52%) vs ERAS 15 (30%),  $p = 0.03$ ] and chronic obstructive pulmonary disease [12 (24%) vs ERAS 4 (8%),  $p = 0.02$ ]. Although the number of patients with ASA class  $> 2$  was higher in the standard group [26 (52%) vs ERAS 15 (30%)], we found no difference between the cohorts in Charlson's comorbidity index. We included these three items, along with age and sex in the subsequent multivariate analyses.

Data on ERAS adherence and compliance for each of the protocol items are shown in Table 2. Adherence to the ERAS protocol was significantly higher in the prospective than in the retrospective cohort [Median: Standard 0.29 (0.14-0.43) vs ERAS 0.71 (0.57-0.82),  $p < 0.001$ ]. The VATS approach was greater in the ERAS group [29 (58%) vs Standard 11 (22%),  $p < 0.001$ ], and the number of patients who ambulated on the first postoperative day [40 (80%) vs Standard 0 (0%),  $p < 0.001$ ], but no difference was found in the use of regional analgesia. Also, the times to oral intake and removal of the urethral catheter were lower in the ERAS group [Median (h): Standard 24 (24-24) vs ERAS (6-7.5), and Standard 48 (24-48) vs ERAS 19 (6-24), respectively].

The primary and secondary results are shown in Table 3. We found no difference between the two groups in either surgical complications [Standard 18 (36%) vs 12 (24%),  $p = 0.19$ ], non-surgical complications [Standard 21 (42%) vs 12 (24%),  $p = 0.06$ ] or length of stay [Median (days): Standard 4 (3-6) vs 4 (3-5),  $p = 0.19$ ], and the ERAS group was significantly lower only in its readmission rate [Standard 15 (30%) vs 6 (12%),  $p = 0.03$ ]. No deaths were recorded in the ERAS group, compared to two deaths in the retrospective cohort.

Multivariate analyses are shown in Figures 1, 2 and 3. ERAS adherence was the only factor associated with a reduction in surgical complications [OR (95%CI) = 0.02 (0.00, 0.59),  $p = 0.03$ , Figure 1A], and postoperative pain [OR (95%CI) = 0.01 (0.00, 0.28),  $p = 0.01$ , Figure 2B]. It was also associated with a lower readmission rate [OR (95%CI) = 0.01 (0.00, 0.24),  $p = 0.007$ , Figure 2A] and an increased likelihood of discharge from the hospital [HR (95%CI) = 18.5 (4.39, 78.4),  $p < 0.001$ , Figure 3]. The thoracic epidural analgesia was the only factor that showed an association with lower rates of non-surgical complications [OR (95%CI) = 0.09 (0.01, 0.49),  $p = 0.008$ , Figure 1B]. It was also associated with lower rates of postoperative pain [OR (95%CI) = 0.16 (0.03, 0.86),  $p = 0.03$ , Figure 2A] and increased probability of discharge from the hospital [HR (95%CI) = 3.14 (1.39, 7.07),  $p = 0.006$ , Figure 3]. The intercostal blockade also increased the latter likelihood [HR (95%CI) = 7.55 (2.94, 19.3),  $p < 0.001$ , Figure 3].

No significant  $p$ -value was rejected after the calculation of  $q$ -value within the multiple comparability study.

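### Three adjustment covariates appear to have been chosen because they differed between cohorts, and the Charlson index appears to have been left out because it did not, although the modelled exposure is adherence

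*SAP*

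**What the plan says.** **Exposure.** The SAP (Statistical analysis) fits the multivariate models on the rate of adherence to ERAS items, "regardless of whether the patients belonged to the ERAS or the retrospective standard cohort". Covariates are described only as clinical and demographic data. There is no list and no rule for choosing them.

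**Available data.** The Protocol (Procedures) states that "Demographic and comorbidity data were collected from all patients" and that the Charlson index was calculated for all of them.

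**Choice of covariates.** The SAP (RESULTS) gives these baseline figures, standard vs ERAS:
- hypertension 26 (52%) vs 15 (30%), p = 0.03
- COPD 12 (24%) vs 4 (8%), p = 0.02
- ASA class > 2 26 (52%) vs 15 (30%), no p-value in the text

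Of Charlson it says "we found no difference between the cohorts in" that index. The next sentence is "We included these three items, along with age and sex in the subsequent multivariate analyses".

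**The concern.** A confounder of the adherence estimates must be related both to adherence and to the outcome. A comparison of the two cohorts does not test that directly. Adherence also varies within each cohort (interquartile range 0.14 to 0.43 in the standard cohort, 0.57 to 0.82 in the ERAS cohort), and several of its items are achieved only after surgery: oral intake, catheter removal, walking and chest tube removal. A sicker patient may miss such items and also do worse. A prognostic factor can therefore matter for the adherence models while being balanced between cohorts, and a non-significant test at 50 per arm does not establish even that balance.

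The favourable conclusion rests largely on these models. The direct cohort comparison of surgical complications was not significant (36% vs 24%, p = 0.19). The adherence models gave OR 0.02 (0.00 to 0.59) for surgical complications, 0.01 for readmission, 0.01 for pain and HR 18.5 for discharge. If a summary of comorbidity was left out, adherence may be credited with some of what healthier patients would achieve anyway.

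**Working it through.** **1. Which three items?** Four variables come before the phrase about three items: hypertension, COPD, ASA > 2 and Charlson. Exactly three are reported as higher in the standard cohort, and Charlson is the one reported as not different. Age and sex were added separately. No comparison of covariates with adherence, and no other reason for the choice, is given.

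**2. The baseline p-values.** The SAP plans a Pearson test. For counts a and b out of 50 each, with s = a + b, χ² = 100(a − b)² / [s(100 − s)].
- Hypertension: 100 × 11² / (41 × 59) = 5.002, p = 0.025. Stated 0.03; agrees.
- COPD: 100 × 8² / (16 × 84) = 4.762, p = 0.029. Stated 0.02; should read 0.03.
- ASA > 2: same counts as hypertension, so p = 0.025.

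All three are below 0.05, which fits selection by cohort difference. The other two-by-two p-values checked (surgical complications 0.190, non-surgical complications 0.056, readmission 0.027) agree with the stated values after rounding.

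**3. How much can a cohort test at 50 per arm show?** The size was set for the primary outcome, not for baseline balance. The stated 47 per arm reproduces: (1.960 + 0.842)² × (0.40 × 0.60 + 0.15 × 0.85) / 0.25² = 46.15, rounded up to 47. The differences below are assumptions, because the text gives no Charlson values.

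| Assumed true difference | Power at 50 per arm, two-sided 5% |
|---|---|
| Standardised difference 0.2 (two means) | 17% |
| Standardised difference 0.3 | 32% |
| Standardised difference 0.5 | 70% |
| 30% vs 40% (exact Pearson) | 18% |
| 30% vs 45% | 34% |
| 20% vs 35% | 39% |
| 10% vs 25% | 53% |
| 5% vs 20% | 66% |

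Charlson is a score, so the first three rows are the closer guide. They approximate the planned Wilcoxon test by a comparison of means.

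**4. Events per model term.** Surgical complications: 18 + 12 = 30. Readmissions: 15 + 6 = 21.

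| Model | Terms | Surgical complications | Readmission |
|---|---|---|---|
| Adherence + five covariates (natural reading) | 6 | 5.0 | 3.5 |
| Same, plus epidural and intercostal block, which have reported estimates | 8 | 3.75 | 2.6 |
| Those eight, with Charlson added | 9 | 3.3 | 2.3 |
| Adherence, age, sex, ASA, Charlson | 5 | 6.0 | 4.2 |
| Same, plus the two blocks | 7 | 4.3 | 3.0 |

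Adding Charlson to everything else worsens an already low ratio. Putting it in place of hypertension and COPD does not.

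**5. The repeated counts.** ASA > 2 and hypertension are both 26 vs 15. If the two were unrelated within each arm, the chance of an exact match in both arms would be at most about Bin(26; 50, 0.52) × Bin(15; 50, 0.30) = 0.1124 × 0.1223 = 0.0137.

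**The case against.** - **The rule is inferred.** The text never says that items entered because they differed. It describes the cohorts and then lists the covariates. The phrase about three items is ambiguous, Charlson is the variable nearest to it, and the forest plots that would show the model terms are not available here. This stands: selection by cohort difference and the omission of Charlson are the natural reading, not established facts.
- **Cohort difference is not irrelevant to adherence.** The medians are 0.29 and 0.71 and the interquartile ranges do not overlap, so a variable that differs by cohort probably relates to adherence too. This also stands. What remains is that the criterion can miss confounding within a cohort and prognostic factors without a significant cohort difference.
- **The frailty argument is limited in the standard cohort.** There, 0 of 50 walked on the first day and time to oral intake was 24 (24 to 24) hours, so those two items scarcely vary. The argument applies mainly to the ERAS cohort and to items such as catheter removal.
- **Overall health is partly adjusted for.** A reader might infer that comorbidity is not adjusted for at all. On the same reading of the text, ASA > 2, COPD, hypertension, age and sex are in the models, and ASA is itself a global measure of health.
- **The power figures depend on what is assumed.** It is tempting to say that two thirds of 15-point imbalances go unnoticed. That holds near 30% vs 45%, but 5% vs 20% would be detected 66% of the time.
- **Replacing the primary covariate set now has its own cost.** It would drop two variables known to be imbalanced, and do so after the results are known. This is a good reason to make the Charlson model a sensitivity analysis.

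**Conclusion.** The point holds in a limited form. On the natural reading, three covariates were entered because they differed between cohorts and Charlson was left out because it did not. Where the exposure is adherence pooled over cohorts, a non-significant difference at 50 per arm is weak ground for omitting a prognostic factor: power is about 17% to 32% for assumed standardised differences of 0.2 to 0.3.

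A reader might go further and conclude that the adherence odds ratios and hazard ratio are biased in favour of ERAS. The documents do not support that. They give no Charlson distribution and no relation of Charlson to adherence, so neither the size nor the direction of any bias can be computed. The direct cohort comparison of the primary outcome is unaffected.

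Nor do the matching ASA and hypertension counts prove an error. The 1.4% bound assumes the two are unrelated, which is unlikely since both describe comorbidity, and the match was noticed before the probability was calculated. It may be a genuine coincidence, but it justifies a check of source records. The missing ASA p-value is missing from the text only; Table 1 is not shown. The COPD p-value is a minor correction that changes no conclusion.

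**What to change.** 1. Check the ASA > 2 counts against source records, and correct the COPD p-value to 0.03 (0.029).
2. List every term in each model, justify the covariates on prognostic grounds, and state whether Charlson was included. If it was, that statement settles the question of its omission.
3. If it was not, re-run all five models (surgical complications, non-surgical complications, readmission, pain, length of stay) as a sensitivity analysis, with Charlson in place of hypertension and COPD and with age, sex and ASA kept. The number of terms does not rise.
4. Report the adherence odds ratios and hazard ratio beside the current ones, and qualify the adherence conclusion if they change materially.

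The cost is one baseline row to verify and five re-runs on variables already collected. The downside is a little more analysis and estimates that may become less favourable.

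### The pooled discharge HR of 18.5 for adherence is in strong tension with the near-equal stays of the two cohorts: its common slope is untested, and it should not be read as the programme's effect on stay

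*SAP*

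**What the plan says.** The SAP's Statistical analysis section sets out two layers. First, the cohorts are compared directly, with "their differences analyzed using the Pearson test or the Wilcoxon rank-sum tests". Second, outcomes are related to adherence "regardless of whether the patients belonged to the ERAS or the retrospective standard cohort"; for stay, "we used Cox regression for multivariate analysis of length of stay". No cohort term is described, and no check that adherence acts alike in the two cohorts.

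RESULTS gives the figures:
- Adherence on a 0-to-1 scale: "Median: Standard 0.29 (0.14-0.43) vs ERAS 0.71 (0.57-0.82").
- The direct comparison of stay: "Standard 4 (3-6) vs 4 (3-5), $p = 0.19".
- The pooled Cox model: adherence associated with "an increased likelihood of discharge from the hospital [HR (95%CI) = 18.5 (4.39, 78.4"), p < 0.001. From the same figure come epidural, HR 3.14 (1.39, 7.07), and intercostal block, HR 7.55 (2.94, 19.3).
- On adjustment: "We included these three items, along with age and sex in the subsequent multivariate analyses".

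The Protocol's Outcomes section lists seven adherence items. Among them are removal of the urinary catheter by 24 hours and of the chest tube by 48 hours. Its Procedures section makes discharge conditional, among other things, on both being out.

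**The concern.** One slope across both cohorts assumes that two kinds of difference in adherence act alike. One is the difference between cohorts, which the programme was meant to create. The other is the difference between patients in the same cohort, which also reflects who recovered well enough to meet the items. Two of the seven items are postoperative events that are also conditions for discharge, so a steep slope among patients treated alike is to be expected even if the programme changes nothing.

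If one slope served both purposes, a rise of 0.42 in median adherence should have shortened stay visibly. The direct comparison shows little. At stake is how the most striking number for stay is used: 18.5 is easily taken to mean that raising adherence brings discharge forward by that much, while the comparison that reflects the programme's change in adherence is compatible with no effect.

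**Working it through.** **Inputs.** HR 18.5 (4.39 to 78.4); median adherence 0.29 and 0.71; stay 4 (3-6) and 4 (3-5) days, p = 0.19 (all SAP, RESULTS); 50 patients per cohort (Protocol, Procedures). Assumptions: the HR is per 0-to-1 unit, medians stand for typical adherence, and there were about 100 discharges (98 if both deaths in the standard cohort preceded discharge).

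**1. The reported HR is internally consistent.** SE = [ln 78.4 − ln 4.39]/3.92 = 0.735. z = ln 18.5/0.735 = 3.97, p = 0.00007, in line with p < 0.001. The model cannot be refitted without patient data.

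**2. Cohort HR implied by the pooled slope.** Difference in adherence: 0.71 − 0.29 = 0.42.
- Point estimate: 18.5^0.42 = 3.41
- Limits: 4.39^0.42 = 1.86 and 78.4^0.42 = 6.25

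Means are not given. A difference of 0.38 would give 3.03 (1.75 to 5.25), and one of 0.45 would give 3.72 (1.95 to 7.12).

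**3. Cohort HR that matches p = 0.19.** z = 1.31. With 100 discharges, HR = exp(1.31 × 2/√100) = 1.30, interval exp[(1.31 ± 1.96) × 0.2] = 0.88 to 1.92. With 98 discharges it is 1.30 (0.88 to 1.94). By the Wilcoxon route, the SE of P(ERAS stay shorter) is √[101/(12 × 2500)] = 0.058. The probability is 0.5 + 1.31 × 0.058 = 0.576, so HR = 0.576/0.424 = 1.36 (0.86 to 2.22). Ties are ignored in both.

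**4. What a raw cohort HR of 3.41 would look like.** P(ERAS shorter) = 3.41/4.41 = 0.773, so the expected z is (0.773 − 0.5)/0.058 = 4.7, p about 0.000002. The ERAS median would lie at 1 − 0.5^(1/3.41) = 18% of the standard cohort's distribution. As the standard lower quartile is 3 days, that means 3 days or less, against 4 reported. At the lower limit, 1.86, the expected z is 2.6 and p about 0.01.

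**5. Simulation.** Step 4 treats a conditional HR as a raw one. Simulating patients avoids this: 50 per cohort, adherence in sevenths, Weibull stays in whole days, one common slope, no other difference between cohorts, 300 runs.
- Slope ln 18.5: median fitted pooled HR 14.3 and raw cohort HR 2.5 (95% of runs 1.7 to 3.9). The raw contrast is thus milder than 3.4, but p ≥ 0.19 occurred in 0 of 300 runs.
- Slope ln 4.39: raw cohort HR 1.7 (1.2 to 2.5); p ≥ 0.19 in about 10% of runs.

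Under other assumed stay distributions the share of runs with p ≥ 0.19 was at most about 1% at 18.5, and between about 10% and 27% at the lower limit.

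**6. Could analgesia technique close the gap?** Bringing 3.41 down to 1.30 needs an offsetting HR of 1.30/3.41 = 0.38. On the log scale this is 0.964, and 0.964/ln 7.55 = 0.48, so about 48 percentage points more intercostal block in the standard cohort, replaced by something without effect. From 1.86 the offset is 0.70, and 0.358/ln 7.55 = 0.18, so about 18 points. With intercostal block assumed in 50% of standard and 0% of ERAS patients, a common slope of ln 18.5 gave p ≥ 0.19 in 73% of runs.

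RESULTS reports no difference in overall regional analgesia, so another technique would have to take its place. If that was epidural, a complete swap offsets only 3.14/7.55 = 0.42, short of the 0.38 needed at the point estimate. At the lower limit, 0.358/ln(7.55/3.14) = 0.41, so a swap of about 41 points would do. In simulation at 18.5, a 50-point swap to epidural gave p ≥ 0.19 in 14% of runs, and a full swap in 54%.

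**The case against.** A reader might infer that the observed stays refute the HR, and that the single slope is therefore wrong. The documents do not support that, for four reasons.

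- The 3.4 is conditional on covariates, while the stay comparison is an unadjusted rank test. A p of 0.19 does not show equal stays, and the upper quartiles were 6 and 5 days.
- The lower limit, 1.86, lies inside the approximate raw interval of 0.88 to 1.92.
- The analgesia techniques have large HRs of their own in the same model. The split by technique is not in the text available, so a shift that masks a true common slope cannot be excluded, though at the point estimate it would have to be extreme.
- The unit is unstated. If adherence was dichotomised, the implied cohort HR depends on the cut, and its direction of change cannot be given here.

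A reader might also infer that 18.5 must come mainly from within-cohort differences. That is the leading explanation, but it is not demonstrated.

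Nor do the documents claim 18.5 as the programme's effect. They word it as an association and report the cohort comparison separately as showing no difference. That is fair, and the point is about how the HR may be read. The baseline imbalances (hypertension, COPD and ASA class above 2 were commoner in the standard cohort) would widen the gap if they lengthen stay. No coefficients for stay are given, however, and the Charlson index did not differ.

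Finally, cohort mean plus deviation is the same fitted model as cohort plus adherence. True, but the two versions report different cohort coefficients, and the centred one gives the adjusted contrast of interest.

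**Conclusion.** The point holds as strong tension. Per 0-to-1 unit, the pooled HR implies a conditional cohort HR of about 3.4 (1.9 to 6.3) against a raw value of about 1.3 (0.9 to 1.9). With a common slope of ln 18.5 and nothing else differing, a Wilcoxon p of 0.19 or more would be seen in at most about 1% of trials; at the lower confidence limit, in about 10% to 27%. Either a slope near its lower limit, a large unreported shift in technique, a period effect, or unequal between- and within-cohort slopes must account for this, and the documents cannot say which. The overlap of postoperative adherence items with the discharge conditions is a likely contributor.

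The common slope is thus untested, and 18.5 should not be used as a measure of what the programme does to stay. This rests on the unit assumed, on medians standing for typical adherence, on about 98 to 100 discharges, and on proportional hazards. No corrected HR can be computed from the documents.

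**What to change.** 1. State the unit of the adherence HR.
2. Refit the Cox model with two terms: the cohort contrast, and each patient's adherence minus the mean of their cohort. Report both HRs with intervals. A common slope requires the log cohort HR to equal the within-cohort slope times the difference in mean adherence, so test that.
3. Check an adherence-by-cohort interaction, that is, whether the within-cohort slopes are equal.
4. Show predicted against observed stay by cohort, and the split of analgesia techniques by cohort.
5. Base any statement about the programme on the covariate-adjusted cohort contrast. Note that it is confounded by calendar period (2016 against 2018-2019) and is not a clean programme effect.
6. Label the within-cohort adherence HR as a descriptive association, and mention the overlap of the catheter and chest-tube items with the discharge conditions.

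The cost is a re-run of one existing model on existing data and some rewording. The downside is a headline HR that is likely to be much less favourable and less precise.
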